## 4.7.4.2. Hepatic Safety

Hepatic laboratory parameters include alanine aminotransferase, aspartate aminotransferase, total bilirubin, serum alkaline phosphatase, and gamma-glutamyltransferase. The central laboratory reference ranges will be used for these laboratory assessments.

If a participant experiences elevated laboratory parameters, as detailed in Section 8.2.11 of the FVAA Protocol, additional tests will be performed to confirm the abnormality. Additional safety data may be collected if required, as defined in the FVAA Protocol. Where applicable, the following will be presented.

The participants' liver disease history and associated person liver disease history data will be listed. Use of acetaminophen during the study, which has potential for hepatotoxicity, will be listed. Results from any hepatic monitoring procedures, such as a magnetic resonance elastography scan, and biopsy assessments will be listed, if performed.

Hepatic risk factor assessment data will be listed. Liver related signs and symptoms data will be summarized by population and treatment, if deemed appropriate, and listed. Alcohol and recreational drug use data will also be listed.

All hepatic chemistry, hematology, coagulation, and serology data will be listed. Values outside the reference ranges will be flagged on the individual participant data listings.

The number and percentage of participants with the following abnormal elevations in hepatic laboratory tests at any time will be summarized between treatment groups:

- an alanine aminotransferase or aspartate aminotransferase measurement of at least 3-fold, at least 5-fold, and at least 10-fold the central laboratory upper limit of normal during the treatment period
- a total bilirubin measurement of at least 2-fold the central laboratory upper limit of normal during the treatment period, and
- an alkaline phosphatase measurement of at least 2.5-fold the central laboratory upper limit of normal during the treatment period.

The number and percentage of participants reporting hepatic events will be assessed using the MedDRA PTs contained in the following Standardized MedDRA Queries (SMQs):

- Broad and narrow terms in the Liver-related investigations, signs and symptoms SMQ
- Broad and narrow terms in the Cholestasis and jaundice of hepatic origin SMQ
- Broad and narrow terms in the Hepatitis noninfectious SMQ
- Broad and narrow terms in the Hepatic failure, fibrosis and cirrhosis and other liver damage-related conditions SMQ, and
- Narrow terms in the Liver-related coagulation and bleeding disturbances SMQ.

When criteria are met for hepatic evaluations, clinicians will complete a follow-up Hepatic Safety eCRF and listings will be provided.

#### 4.7.6. Other Assessments

All other safety assessments not detailed in this section will be listed but not summarized or statistically analyzed.

## 4.8. Other Analyses

## 4.8.1. Endpoint Definitions

Primary and secondary endpoint definitions are provided in the table below.

Measu re	Description	Variable	Derivation and Comment	Imputation Approach if with Missing Components
PASI	PASI: Combines clinician-reported assessments of the extent of body-surface involvement in 4 anatomical regions (head and neck, trunk, arms, and legs) and the severity of scaling (S), redness (R), and plaque induration and infiltration (thickness, T) in each region, yielding an overall score of 0 for no psoriasis to 72 for the most severe disease (Fredriksson and Pettersson 1978).  Severity is rated for each index (R, S, T) on a 0-4 scale (0 for no involvement up to 4 for very severe involvement):  0 = none  1 = slight  2 = moderate  3 = severe  4 = very severe  The body is divided into 4 anatomical regions comprising the head (h), upper limb (u), trunk (t), and lower limb (l). In each of these areas, the fraction of total BSA affected is graded on a 0-6 scale (0 for no involvement; up to 6 for 90%-100% involvement):  0 = 0% (clear)  1 = >0% to <10%  2 = 10% to <30%  3 = 30% to <50%  4 = 50% to <70%  5 = 70% to <90%	PASI score	The composite PASI score is calculated by multiplying the sum of the individual severity scores for each area by the weighted area-of-involvement score for that respective area, and then summing the 4 resulting quantities as follows: PASI = 0.1(R h + T h + S h )A h + 0.2(R u + T u + S u )A u + 0.3(R t + T t + S t )A t + 0.4(R l + T l + S l )A l where,  R h , R u , R t , R l = redness score of plaques on the head, upper limb, trunk, and lower limb, scored 0-4 respectively; T h , T u , T t , T l = thickness score of plaques on the head, upper limb, trunk, and lower limb, scored 0-4 respectively; S h , S u , S t , S l = scaliness score of plaques on the head, upper limb, trunk, and lower limb, scored 0-4 respectively; A h , A u , A t , A l = numerical value translation of percentage area of psoriatic involvement score for the head, upper limb, trunk, and lower limb, respectively. PASI scores are treated as a continuous score, with 0.1 increments within these values.	If any individual score is missing, the PASI score will not be calculated, hence missing.
	6 = 90% to 100%  The various body regions are weighted to reflect their respective proportion of BSA.	PASI change from baseline	Calculated as: observed PASI – baseline PASI.	Missing if baseline or observed value is missing.

Measu re	Description	Variable	Derivation and Comment	Imputation Approach if with Missing Components
		PASI percent improveme nt from baseline	Calculated as:  Percent improvement from baseline  =  100  **Baseline PASI - Observed PASI**  Baseline PASI  If a patient has experienced an improvement, this measure will be positive. If a patient has experienced a worsening in the condition, this measure will be negative.	Missing if baseline or observed value is missing.
		PASI 75 (Primary)	A clinically meaningful response; at least a 75% improvement in PASI score from baseline.	Missing if baseline or observed value is missing.
		PASI 90	Higher level of clearance; at least a 90% improvement in PASI score from baseline.	Missing if baseline or observed value is missing.
		PASI 100	Complete resolution of plaque psoriasis; a 100% improvement in PASI score from baseline.	Missing if baseline or observed value is missing.
	sPGA: The physician's global	sPGA score	Range from 0 to 5: clear (0), almost clear (1), mild (2), moderate (3), severe (4).	Single item, missing if missing.
sPGA	assessment of the patient's psoriasis lesions at a given time point. Plaques are graded for plaque elevation, scaling, and erythema on a range of clear (0),	sPGA (0,1)	An sPGA assessed as either 0 or 1, which represents a clinically meaningful response of minimal plaque severity or complete resolution of plaque psoriasis.	Missing if sPGA is missing.
	almost clear (1), mild (2), moderate (3), and severe (4).	sPGA (0)	An sPGA assessed as 0, which represents a clinically important endpoint indicating complete resolution of plaque psoriasis.	Missing if sPGA is missing.

Measu re	Description	Variable	Derivation and Comment	Imputation Approach if with Missing Components
	Percentage of BSA: The investigator will evaluate the percentage involvement of psoriasis on each patient's BSA on a continuous scale from 0% (no involvement) to 100% (full involvement), in which 1% corresponds to the size of the patient's hand (including the palm, fingers, and thumb) (Van Voorhees et al. 2016)	BSA	Collected as a single scale as part of PASI electronic case report form eCOA. Range from 0% to 100%.	Single item, missing if missing.
BSA		BSA change from baseline	Calculated as: observed BSA – baseline BSA.	Missing if baseline or observed value is missing.
The PSS is a patient-reported, 8-item scale used in adults. It is based on the assessment of  • 4 symptoms: itch, pain, stinging, and burning  • 3 signs: redness, scaling, and cracking  PSS  • 1 item on the discomfort related to	PSS item scores	The PSS item scores will be collected during office visits.	The item is missing if it is not present in the data.	
	PSS Symptoms Score	Calculated by summing the individual item scores as follows: itch NRS + pain NRS + stinging NRS + burning NRS.	If any of the 4 relevant item scores are missing, the score is missing.	
	symptoms/signs (Armstrong et al. 2020). Respondents are asked to answer the questions based on their psoriasis symptoms in the past 24 hours.	PSS Signs Score	Calculated by summing the individual item scores as follows: redness NRS + scaling NRS + cracking NRS.	If any of the 3 relevant item scores are missing, the score is missing.

Measu re	Description	Variable	Derivation and Comment	Imputation Approach if with Missing Components
	The overall severity for each individual symptom from patient's psoriasis is indicated by selecting the number from an NRS of 0 to 10 that best describes the worst level of each symptom in the area in the past 24 hours, where 0 (no severity) and 10 (worst imaginable severity).  The symptom severity scores, ranging from 0 to 10, are the values of the selected numbers indicated by the patient on the instrument's horizontal scale. Each of the 8 individual items will receive a score of 0 to 10 and will be reported as item scores for itch, pain, discomfort, stinging, burning, redness, scaling, and cracking.	PSS (Signs, Symptoms, items) Score change from baseline	Change from baseline = Observed PSS Score — Baseline PSS Score Here "PSS Score" could refer to the Signs, Symptoms, or an item Score. Negative change indicates improvement, and a positive change indicates deterioration of the condition.	Missing if either observed or baseline PSS score is missing.

Measu re	Description	Variable	Derivation and Comment	Imputation Approach if with Missing Components
	PSSI is a clinician-reported assessment to be used if the patient has scalp psoriasis at baseline. The scalp will be assessed for erythema (redness), induration (hardness), and desquamation (shedding of skin) and percentage of area affected	PSSI score	The PSSI score is a composite score derived from the sum of the scores for erythema, induration, and desquamation multiplied by the score for the extent of scalp area involved (percent of scalp involved). The range is 0 to 72.	If any individual score is missing, the PSSI score will not be calculated, hence missing.
	as follows: Erythema, Induration and Desquamation: 0 = Absent	PSSI score change from baseline	Calculated as: observed PSSI – baseline PSSI.	Missing if baseline or observed value is missing.
PSSI	1 = Slight 2 = Moderate 3 = Severe 4 = Severest Possible Percent of Scalp Involved: 0 = none 1 = <10% 2 = 10-29% 3 = 30-49% 4 = 50-69% 5 = 70-89% 6 = 90-100% (Thaçi et al. 2015)	PSSI score of 0	A PSSI response is defined as a PSSI score of 0, which is also referred to as scalp clearance.	Missing if PSSI score is missing.
DLQI	The DLQI is a validated, dermatology-specific, patient-reported outcomes assessment that evaluates patient's health-related QoL. This questionnaire has 10 items that are grouped in 6 domains, including symptoms and feelings, daily activities, leisure, work and school, personal relationships, and treatment. The recall period of this scale is over the "last week."	DLQI total score	A DLQI total score is calculated by summing all 10 question responses and has a range of 0 to 30 (less to more impairment) (Finlay and Khan 1994; Basra et al. 2015).	If 2 or more questions are missing, the total score is missing. Note: #7B could be a valid missing when #7A is not "No." That is, #7 should be considered as 1 question.
	Response categories and corresponding scores are  Very much = 3  A lot = 2  A little = 1  Not at all = 0  Not relevant = 0	DLQI total score and domain scores change from baseline	Calculated as: observed DLQI (total score or domain scores) – baseline DLQI (total score or domain scores).	Missing if baseline or observed value is missing.

Measu re	Description	Variable	Derivation and Comment	Imputation Approach if with Missing Components
PatGA	The PatGA is a patient reported, single item scale on which patients are asked to rank, by selecting a number on a 0-to-5 NRS, the severity of their psoriasis "today" from 0 (clear), no psoriasis, to 5 (severe).	Change from baseline	Change from baseline = Observed Item PatGA score – Baseline Item PatGA score.	Missing if baseline or observed value is missing.

Abbreviations: BSA = body surface area; DLQI = Global Assessment Dermatology Life Quality Index; eCOA = electronic Clinical Outcome Assessment; NRS = numeric rating scale; PASI = Psoriasis Area and Severity Index; PatGA = Patients Global Assessment of Psoriasis; PSS = Psoriasis Symptoms Scale; PSSI = Psoriasis Scalp Severity Index; QoL = quality of life; sPGA = Static Physician Global Assessment.

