#### Handling of missing, unused, and spurious data

Handling of missing, unused, and spurious data is addressed prospectively in the overall statistical methods described in the protocol and in this document, where appropriate. Adjustments to the planned analyses are described in the final clinical study report.

Missing data imputation is not to be confused with estimand strategy. Missing data of categorical efficacy, patient-reported outcomes, and quality-of-life variables will be imputed using a nonresponder imputation (NRI) method, and the missing data will be considered as nonresponder. For continuous variables, missing data will not be imputed.

When NRI is applied, participants with missing data will be considered as nonresponders regardless of whether they have at least 1 postbaseline data.

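### The SAP sets PASI and PSSI to missing for any blank item, with no exception where a recorded area of 0 already fixes the product at 0, so NRI could count a clear participant as a non-responder

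*SAP*

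**What the plan says.** SAP Section 4.8.1 builds PASI by "multiplying the sum of the individual severity scores for each area by the weighted area-of-involvement score" for each of four regions (weights 0.1, 0.2, 0.3 and 0.4) and adding the four products, "yielding an overall score of 0 for no psoriasis to 72 for the most severe disease". The area grade runs from 0 (clear) to 6. PSSI is the sum of erythema, induration and desquamation "multiplied by the score for the extent of scalp area involved (percent of scalp involved). The range is 0 to 72". Its extent grade also starts at zero: "Percent of Scalp Involved: 0 = none".

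The missing-component rules in the same table are:
- PASI: "If any individual score is missing, the PASI score will not be calculated, hence missing".
- PSSI: "If any individual score is missing, the PSSI score will not be calculated, hence missing".
- PASI 75, 90 and 100: "Missing if baseline or observed value is missing". PSSI 0 is likewise missing when PSSI is missing.

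Under the missing-data heading of SAP Section 4.1, "participants with missing data will be considered as nonresponders regardless of whether they have at least 1 postbaseline data". Continuous values are not imputed. SAP Sections 4.3 and 4.4 apply NRI to the primary endpoint and to the binary secondary endpoints.

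**The concern.** Where the recorded area is 0, the severity items carry no information about the score. Treating the total as missing when one of them is blank discards a value that the data already determine. NRI then turns that loss into a failure. A participant with all four areas recorded as 0 and the severities blank would count as a PASI 75 non-responder.

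Full clearance is not needed. One clear region with blank severities removes the whole PASI, so a PASI 75 or PASI 90 responder with residual plaque elsewhere is also at risk. PASI 100 and PSSI 0 are most exposed, because every PASI 100 responder with complete data has a zero product in all four regions and every PSSI 0 responder has a zero product on the scalp. For the continuous endpoints, the value leaves the MMRM at that visit for a reason related to clearance.

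The same table does allow for a logically empty item elsewhere: DLQI item 7B may be validly blank depending on item 7A. PASI, which carries the primary endpoint, and PSSI have no such provision.

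**Working it through.** **1. Reproduce the stated ranges.** Each of three severity signs is graded 0 to 4 (maximum sum 12), and area or extent is graded 0 to 6.
- PASI maximum = (0.1 + 0.2 + 0.3 + 0.4) × 12 × 6 = 72.
- PSSI maximum = 12 × 6 = 72.

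Both match the SAP.

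**2. Set the area to 0.** The regional PASI term is weight × (R + T + S) × 0 = 0, and PSSI = (sum of signs) × 0 = 0. This holds for all 5 × 5 × 5 = 125 severity combinations. For PASI it fixes only that region's term; the total is 0 only when all four areas are 0.

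**3. Apply the rules to constructed cases.** Illustrative baseline: head 0.1 × 6 × 2 = 1.2; upper limb 0.2 × 7 × 2 = 2.8; trunk 0.3 × 8 × 2 = 4.8; lower limb 0.4 × 8 × 3 = 9.6; total 18.4.

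| Week 12 record | SAP rule plus NRI | Area 0 scored as 0 |
|---|---|---|
| All four areas 0, severities blank | Missing, non-responder | PASI 0, 100% improvement, responder on PASI 75/90/100 |
| Head area 0, severities blank; other regions 0.2×2×1 + 0.3×3×1 + 0.4×3×1 | Missing, non-responder | PASI 0.4 + 0.9 + 1.2 = 2.5; (18.4 − 2.5)/18.4 = 86.4%, PASI 75 responder |
| Scalp extent 0, severities blank | Missing, non-responder for PSSI 0 | PSSI 0, responder |
| Area above 0, one severity blank | Missing | Missing (unchanged) |

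**4. Size, by assumption only.** Arm sizes, response rates and power are redacted in SAP Section 5. If a share q of true responders is affected equally in both arms, each rate and the difference are multiplied by (1 − q). Assume 40% vs 5%, 25 per arm, one-sided 0.025 (the SAP's level). The columns give normal-approximation power and exact enumeration of the unstratified CMH statistic:

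| q | Rates | Difference (points) | Power, approximation | Power, exact |
|---|---|---|---|---|
| 0 | 40% vs 5% | 35 | 0.87 | 0.91 |
| 5% | 38% vs 4.75% | 33.25 | 0.84 | 0.89 |
| 10% | 36% vs 4.5% | 31.5 | 0.81 | 0.86 |
| 20% | 32% vs 4% | 28 | 0.75 | 0.81 |

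Each affected responder costs 1/25 = 4 points in an arm of 25.

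**5. Direction.** NRI can only turn a responder into a non-responder, so each arm's rate can only fall. With unequal shares, the difference changes by −(p_active × q_active − p_placebo × q_placebo). At 40% vs 5%, the difference would widen only if the placebo share exceeded 0.40/0.05 = 8 times the active share.

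**The case against.** The strongest reply is that the SAP already gives clear skin a severity value: grade 0 means none for each PASI sign and absent for each PSSI sign. A clear region completed as defined is recorded as 0, 0, 0; the score computes, and the participant is a responder. A reader might infer that severity is ungradable where there is no plaque, so that blanks are the normal record of clear skin. The documents do not support that. Blanks arise only from an omitted entry or from a form that skips the items.

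Whether the form forces, auto-fills or skips them is not in either document. The protocol (Schedule of Activities; Section 10.1.7) says only that these assessments are captured electronically and that the electronic record is the source. That leaves the size open. It also means that a blank has no separate site record from which to complete it.

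Systematic blanks might well surface early. A PASI total is needed for eligibility at Visits 1 and 2 (protocol Section 5.1), and any participant with an uninvolved region would test the form then. This is a reasonable inference, but it does not cover occasional omissions at Week 12.

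A reader might also infer that the loss falls mainly on the active arm as a mechanism of its own. Regions can be clear from baseline, where randomization balances them in expectation, and a PASI 75 responder need not have any clear region. What stands is narrower: losses under NRI come only from would-be responders, so an arm with more responders has more to lose.

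**Conclusion.** The point holds as a gap in the scoring rule. As written, the SAP treats a determined score as missing and then as a failure whenever severity items are blank in a region recorded as clear. PSSI 0 and PASI 100 are most exposed, and the likely direction is toward no effect.

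The documents do not support the stronger conclusion that the primary analysis is biased. They do not show that such blanks occur, and if the form enforces or fills the items the effect is nil. The rates, arm size and loss shares used above are assumptions. On them, a 5% loss of responders costs about 2 to 3 points of power; nothing in the documents makes a 20% loss plausible. The case for acting is that the correction is specific and nearly free, while a misclassified primary outcome is hard to defend after unblinding.

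**What to change.** Before unblinding, replace the two missing-component rules in SAP Section 4.8.1 with:

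*If a region's area score is recorded as 0, that region contributes 0 to PASI whether or not its severity items are recorded; if the PSSI extent score is recorded as 0, PSSI = 0. Otherwise the score is missing if an area or extent score is missing, or if a severity item is missing where the area or extent score is above 0.*

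Confirm from the electronic form's specification whether severity items are mandatory, auto-filled or skipped when the area is 0, and state the answer in the SAP. Query any area of 0 with blank severities that conflicts with BSA or sPGA at the same visit; the Schedule of Activities collects both wherever PASI is scheduled from screening through follow-up, apart from the optional PASI at unscheduled visits.

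The cost is two SAP sentences, one derivation line and one data check. There is a small downside: a mis-keyed area of 0 on an incomplete form could count as clear. The cross-check limits this. It works best for a false whole-body zero and less well for a single region while disease remains elsewhere.

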## 4.8.2. Subgroup Analyses

Subgroup analyses of the primary endpoint and secondary endpoints will be made to assess consistency of the intervention effect across the following subgroups:

- age group: younger than 65 versus 65 years or older
- sex: female versus male
- ethnicity: Hispanic or Latino versus Non-Hispanic or Latino
- race: White versus Black versus Other
- prior exposure to biologic therapy: biologic naïve versus biologic experienced, and
- body mass index: less than 30 versus 30 or greater.

If the number of participants is too small (less than 10%) within a subgroup, then the subgroup categories may be redefined prior to unblinding the study.

# 4.9. Interim Analyses

Analyses for the primary database lock will be conducted as described in Section 9.3 of the protocol. If Stage 2 is not initiated, the primary outcome database lock will occur when all the participants from Stage 1 have completed the Week 12 visit or have discontinued the study intervention. If Stage 2 is initiated, the primary outcome database lock will occur when all the participants from Stage 2 have completed the Week 12 visit or have discontinued the study intervention.

Two interim analyses may be conducted during Stage 1 prior to the primary database lock at the sponsor's discretion. One interim may occur when approximately 50% to 90% of participants from Stage 1 have completed the Week 12 visit or have discontinued the study intervention. Another interim analysis may be conducted when approximately 90% to 100% of participants from Stage 1 have completed the Week 12 visit or have discontinued the study intervention. The results of either interim analysis can be used by the sponsor's internal assessment committee (IAC) to recommend if Stage 2 should be initiated.

The interim analyses may include safety, PK, PD, and efficacy data. The data may be used for internal decision making, development of PK and PD modeling, or both. An assessment of unblinded interim data will be conducted by an IAC with a limited number of individuals who do not have direct site contact or data entry or validation responsibilities. Study sites will receive information about interim results only if they need to know for the safety of their participants.

The study will not be stopped early due to efficacy.

Unblinding details are specified in the blinding unblinding document.

At the discretion of the sponsor, prespecified interim analyses may not be conducted.

